9.5 Handling of Missing Data

9.5.1 Missing Data for Continuous Endpoints

Drinking data is collected in the TLFB. Prior to the subject dropping out of the study, every attempt will be made to continue to collect TLFB data. However, if the subject no longer wishes to participate in the collection of the TLFB, but agrees to a shorter drinking assessment using the Brief Drinking Questionnaire (BDQ), then, answers from the BDQ will be used in conjunction with the TLFB (if some TLFB data were provided by the subject) or in lieu of the TLFB (if no data were provided by the subject) to otherwise avoid missing data for drinking endpoints. Specifically, the BDQ has two questions assessing whether the subject had any heavy drinking days or drinking days during the period covered and will be used to assess the presence of a heavy drinking day or or a drinking day, respectively, for the drinking endpoints percentage of subjects with no heavy drinking days and percentage of subjects abstinent, respectively.

The primary analysis of the primary endpoint will be performed on available data in the Full Analysis Set with no imputation for missing data. However, a sensitivity analysis will be performed on the primary endpoint using multiple imputation for missing drinking data (Jakobsen et al, 2017). Multiple imputation replaces each missing value with a set of "m" plausible values that represent the uncertainty about the right value to impute. The multiple imputation method will be performed on transformed endpoint data, if a transformation is deemed necessary. The data will be evaluated for the pattern of missingness. If the data have monotone missingness then the regression method will be used. If the data have non-monotone missingness then the Monte Carlo method will be used (Ratitch et al, 2013). The imputation model will include a limited set of variables likely to be associated with missingness on the primary endpoint, excluding treatment assignment. The variables may include but are not limited to site, time and baseline alcohol use. The "m" imputed datasets each will be analyzed using mixed effects models then SAS PROC MIANALYZE will be used to combine the parameter estimates.

No imputation will be done for analysis of secondary endpoints.

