# 10.12. Brief Drinking Questionnaire

If a subject is withdrawn from the study early and is no longer participating in clinic visits or providing TLFB drinking data but is willing to be contacted by phone at the week most proximal to dropout, then they will be administered the Brief Drinking Questionnaire. The questions are taken from the list recommended by the NIAAA Task Force on Recommended Alcohol Questions (Oct 15-16, 2003) and ascertain: if there was any drinking during the target period; if so, how many a day on average; the largest number of drinks consumed on any one day; and, the number of times reaching the heavy drinking limit (4 or more for women and 5 or more for men). This data will be recorded on a source document and eCRF. This does not apply to subjects who are willing to supply daily drinking data by the TLFB method.

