# 11.4.2. Analysis Addressing the Primary Efficacy Endpoint

The analysis of the primary endpoint will be a mixed-effect model for repeated measures. Treatment group, study week, treatment group by study week interaction, clinical site and baseline percentage of heavy drinking days will be covariates in the mixed effects model. Additional covariates may be selected as specified in the SAP. The primary endpoint will be performed on available data in the Full Analysis Set with no imputation for missing data. A sensitivity analysis will be performed using multiple imputation for missing drinking data (*Jakobsen-2017*). Multiple imputation replaces each missing value with a set of "m" plausible values that represent the uncertainty about the right value to impute. The imputation model will include a limited set of variables likely to be associated with missingness on the primary endpoint, excluding treatment assignment. The variables may include but are not limited to site, time and baseline alcohol use. Specification of the variables used in the multiple imputation models will be provided in the SAP.

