3.2 Study Design

This study is a double-blind, randomized, placebo-controlled, parallel group, multi-site clinical trial designed to assess the efficacy of oxytocin compared with placebo to reduce drinking in 100 subjects (50 in each group) who report 4 or more Diagnostic and Statistical Manual of Mental Disorders – Fifth Edition (DSM-5TM) symptoms of AUD. This study will be conducted at 4 clinical sites. If eligible for the study, subjects will be randomized using a stratified permuted block randomization procedure with "clinical site" as a stratification variable in an approximate 1:1 ratio (targeting 50 subjects per group) to receive either intranasal oxytocin or placebo for 12 weeks.

[figure not shown]
If eligible for the study, subjects will receive blinded intranasal oxytocin at 35 IU once per day or intranasal placebo (same volume once per day) for 2 weeks (initial tolerability assessment period), then for the next 10 weeks (maintenance period) subjects will receive oxytocin at 35 IU/twice per day (BID, totally daily dose 70 IU) or intranasal placebo (same volume twice per day)

Subjects will be seen in the clinic at screening visit(s), at randomization, and at Weeks 2, 3, 4, 6, 8, 10, and 13. During the alternate weeks when subjects will not be coming into the clinic (Weeks 5, 7, 9, 11, and 12), subjects will be contacted once during that week by telephone to encourage study drug compliance and to assess withdrawal, adverse events (AEs), and concomitant medication use. A final follow-up telephone interview will occur during Weeks 14/15 (1-to-2 weeks after the end of dosing).

Enrollment will be halted if 2 or more at least possibly related SAEs as judged by the investigator or medical monitor occur. If this occurs, a DSMB meeting will be convened and a decision, in conjunction with the study Sponsor, will be made regarding stopping the study.

The overall study schema is provided in Figure 1. The study schedule of visits and assessments is shown in Table 1.

Figure 1. Overview of Study Design

*Telephone contact, otherwise visit is in clinic

Oxytocin for Alcohol Use Disorder Protocol Number: NCIG-007R

Table 1. Schedule of Assessments

	Screen						ľ	Mainte	nance					EOS ^a	Safety Follow-up
Study Week	-2 to -1	1	2	3	4	5	6	7	8	9	10	11	12	13	14/15
Clinic Visit #	1	2	3	4	5		6		7		8			9	
Informed Consent	X														
Alcohol Breathalyzer	X	X	X	X	X		X		X		X			X	
Urine Drug Screen ^b	X	X	X	X	X		X		X		X			X	
Locator Form	X														

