7.0 SAMPLE SIZE CONSIDERATIONS

With an intake sample of 100 subjects (50 subjects per arm) and 12% attrition, it is projected that the sample size for primary endpoint analyses will be 88 (44 subjects per arm). The alpha level for the primary analyses will be 0.05, two-tailed. An estimate of the effect size (Cohen's d) for the investigational products is 0.60. Equal variances in both groups are assumed. These assumptions lead to a projected power of 0.80.

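### The only sensitivity analysis planned for missing primary data still assumes missing at random, so no planned analysis tests whether the result survives dropouts who relapse

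*SAP*

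**What the plan says.** The primary endpoint is the weekly percentage of heavy drinking days (PHDD) over study weeks 3 to 12. SAP 9.4.1 and 9.5.1 analyse it with a repeated-measures mixed model on available data, without imputation.

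One further analysis addresses missing values. Protocol 11.4.2 states: "A sensitivity analysis will be performed using multiple imputation for missing drinking data". SAP 9.5.1 repeats this ("a sensitivity analysis will be performed on the primary endpoint using multiple imputation for missing drinking data") and adds the method: regression if missingness is monotone, Monte Carlo if it is not, on the transformed scale if a transformation is used. Treatment is excluded from the imputation model. The list of other variables is left open, with site, time and baseline alcohol use as examples. SAP Table 25 is the only matching output.

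Neither document specifies a delta adjustment, a tipping point, a reference-based rule or a rule that counts missing days as heavy drinking. A paper on pattern-mixture models is cited in SAP 9.5.1, but only beside the Monte Carlo method.

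For subjects who withdraw and decline the Timeline Followback (TLFB), Protocol 10.12 provides a Brief Drinking Questionnaire that records, among other things, "the number of times reaching the heavy drinking limit". SAP 9.5.1 describes two questions, on whether there were any drinking days or any heavy drinking days, and uses them for two dichotomous secondary endpoints. SAP Listing 17 holds only yes/no answers.

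**The concern.** An available-data mixed model and an unshifted imputation both predict unseen weeks from what was observed. If subjects leave because their drinking is getting worse, the weeks after exit may be heavier than any earlier data predict, and both analyses would miss this in the same direction.

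The sponsor's own documents treat such exits as possible. Protocol 7.16 gives increased drinking as its first example of a situation requiring discontinuation from the study. The disposition shell (SAP Table 1) provides for perceived lack of efficacy, clinical deterioration and preference for another treatment as reasons for leaving.

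At stake is what a significant primary result could claim. Agreement between Tables 24 and 25 could be read as robustness to dropout, although Table 25 cannot show how much worse dropouts would have to be to overturn the result.

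**Working it through.** **Inputs from SAP 7.0** (also Protocol 11.5). "The alpha level for the primary analyses will be 0.05, two-tailed"; Cohen's d "for the investigational products is 0.60"; "Equal variances in both groups are assumed"; 100 subjects, 12% attrition, 44 analysed per arm. No SD in PHDD points is given, so everything below is in SD units of the 10-week mean. Shift sizes and dropout shares other than 12% are assumptions.

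**1. The plan's own figure.** "These assumptions lead to a projected power of 0.80". Check: z = 0.60/√(2/44) = 2.81; power = Φ(2.81 − 1.96) = 0.804 (0.795 by noncentral t). It reproduces. An observed d of 0.60 at 44 per arm has p of about 0.005.

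**2. Tipping point, oxytocin dropouts only.** With 50 per arm, the smallest significant d is t(0.975, 98) × √(2/50) = 0.397. Adding δ to a share m of the oxytocin arm lowers d by mδ, so the tipping shift is δ* = (d − 0.397)/m.

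| Observed d | m = 6% | m = 12% | m = 18% | m = 24% |
|---|---|---|---|---|
| 0.60 | 3.39 | 1.69 | 1.13 | 0.85 |
| 0.50 | 1.72 | 0.86 | 0.57 | 0.43 |
| 0.45 | 0.89 | 0.44 | 0.30 | 0.22 |

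The 12% column treats dropouts as missing for all ten weeks. If they miss half the weeks on average, the 6% column applies. Measured from the placebo mean, 1.69 SD is 1.69 − 0.60 = 1.09 SD.

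The limit of 0.397 credits imputed subjects with full information. The limit at 44 per arm is t(0.975, 86) × √(2/44) = 0.424, which gives (0.60 − 0.424)/0.12 = 1.47 and (0.45 − 0.424)/0.12 = 0.22. The figures are therefore approximate.

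**3. The same case measured from the placebo mean.** If the 6 oxytocin dropouts average Δ above the placebo mean and placebo dropouts sit at it, d = 0.60 − 0.12 × (0.60 + Δ) and z = d/0.20.
- Δ = 0.5: d = 0.468, p = 0.019
- Δ = 1.0: d = 0.408, p = 0.041
- Δ = 1.5: d = 0.348, p = 0.082

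**4. Both arms.** A common shift changes d by δ × (placebo share missing − oxytocin share missing).
- Equal dropout with an equal shift leaves d at 0.60.
- If dropouts in both arms end at the same level, whatever it is, d = 0.88 × 0.60 = 0.53, z = 2.64, p about 0.008.

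**5. Would the planned imputation register relapse?** This was simulated with ten weekly values, an assumed intraclass correlation of 0.6, dropout at a random week, planned d of 0.60 and a rise of 2 units after exit. A unit is the SD of the 10-week mean. The weekly SD is √(1/(0.6 + 0.4/10)) = 1.25, so the rise is 2/1.25 = 1.6 weekly SD. Imputation with treatment stands in for the primary model.

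| Dropout, oxytocin / placebo | True d | Imputed with treatment | Imputed without treatment (SAP) |
|---|---|---|---|
| 12% / 12% | 0.60 | 0.60 | 0.59 |
| 18% / 6% | 0.48 | 0.60 | 0.59 |
| 24% / 0% | 0.37 | 0.61 | 0.60 |

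With no relapse, the two imputations differed by the same 0.01 or so. Leaving treatment out is therefore not a test of relapse.

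**The case against.** The plan's main defence is to collect the data. Protocol 7.14 keeps subjects who stop study drug in the study with all assessments. Protocol 10.32 requires missed drinking data to be collected at the next visit and allows telephone TLFB after withdrawal. SAP 5.1.5 counts a week with three observed days. Retention, participation and reasons for leaving are reported by arm. All of this stands and limits the exposure, although telephone follow-up needs the subject's agreement and the sponsor still plans for 12% attrition.

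A reader might infer that the imputation merely repeats the primary model's assumption. The documents do not support that exactly: the mixed model conditions on treatment and treatment by week, while the imputation excludes treatment and may add variables. But more variables give no departure from missing at random.

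A reader might also infer that dropout must bias the result towards oxytocin. Nothing in the documents suggests that relapse would differ between blinded arms, and bias in the contrast needs unequal dropout or unequal relapse. Whether they are equal cannot be known in advance, which is the reason to pre-specify a range.

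Protocol 11.4.11 calls this a pilot study. It says so to excuse unadjusted secondary comparisons; it does not bear on an untested assumption behind the primary result.

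**Conclusion.** The gap is real and moderate in size. Both analyses of the primary endpoint rest on missing at random; neither document uses the phrase, but the assumption follows from the methods named.

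At the planned effect with 12% missing throughout, the result is fairly robust: it takes a relapse of about 1.7 SD confined to oxytocin dropouts, or about 1.1 SD above the placebo mean, to lose significance. At d of about 0.45 roughly 0.4 SD is enough, and larger dropout in the oxytocin arm lowers the threshold further. These figures rest on a normal approximation, equal variances and assumed shifts. Without an SD in PHDD points, it cannot be said whether 1.7 SD lies within a return to baseline drinking.

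Two stronger readings should be avoided. One is that a positive result would carry no evidence about dropouts: retention, reasons for leaving and the questionnaire-based secondary endpoints would all be reported. The other is that the SAP discards heavy-day counts it holds: the documents disagree on whether the questionnaire yields counts at all.

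**What to change.** Before unblinding, add to SAP 9.5.1 a delta-adjusted (pattern-mixture) imputation of the primary endpoint:

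- Shift imputed post-dropout weeks upward in fixed steps of PHDD points, on the untransformed scale and capped at 100%, up to a return to baseline PHDD.
- Apply the shifts first in both arms, then in the oxytocin arm only.
- Report the estimate at each step and the shift at which two-sided p exceeds 0.05.

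Separately, reconcile the Brief Drinking Questionnaire: Protocol 10.12 records a heavy-day count, while SAP 9.5.1 and Listing 17 show two yes/no questions. Use counts to judge which shifts are credible only if they were captured; the table works without them.

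The cost is one more table and some programming beyond the planned imputation code: back-transformation where a transformation was used, the cap, and arm-specific shifts applied after an imputation that excludes treatment. The oxytocin-only result can only look equal or less favourable. The both-arm result can move either way, and would favour oxytocin if placebo loses more subjects.

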9.4 Efficacy Analysis

9.4.1 Primary Analysis of Primary Efficacy Endpoint

The primary efficacy endpoint is the weekly percentage of heavy drinking days during the 10-week maintenance period (study weeks 3-12). The primary analysis of the primary endpoint will be a fully covaried, mixed-effect model for repeated measures employed on the Full Analysis Set (using an appropriate transformation of the endpoint, if needed; see Section 9.1). Treatment group, study week, treatment group by study week interaction, clinical site and baseline percentage of heavy drinking days will be covariates in the mixed effects model. The analyses will be performed using SAS PROC MIXED procedure Subjects are treated as a class variable and not continuous. The week, treatment group, and clinical site are also treated as class variables. Additional covariates may be selected using the method described in Section 9.4.3. The solution statement from SAS PROC MIXED is requested to provide the solution for the fixed effects parameters. A REPEATED statement specifies that values are repeated each week and subjects are nested within treatment group. The covariance structure is specified.

The selection of the covariance structure is performed using a simple repeated mixed effects model that includes treatment group as the only fixed effect and subject nested within treatment group as the only random effect. The covariance structure is selected from autoregressive, compound symmetry, Toeplitz, and unstructured. The Akaike Information Criterion (AICc) corrected for a finite sample is obtained from each of the four models for the four possible covariance structures to determine model fit. The smallest (minimum) AICc associated with one of the covariance structures is selected and the difference for each of the other three covariance structures is calculated. A graph is produced of the model fit statistics and relative difference for the four possible covariance structures.

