Placebo	8	XX.XX	0.xxx	0.xxx	0.xxx						
Oxytocin	9	XX.XX	0.xxx	0.xxx	0.xxx	X.XXX	X.XXX	0.xxx	XX.XXX	0.xxx	XX.XXX
Placebo	9	XX.XX	0.xxx	0.xxx	0.xxx						
Oxytocin	10	XX.XX	0.xxx	0.xxx	0.xxx	X.XXX	X.XXX	0.xxx	XX.XXX	0.xxx	XX.XXX
Placebo	10	XX.XX	0.xxx	0.xxx	0.xxx						
Oxytocin	11	XX.XX	0.xxx	0.xxx	0.xxx	X.XXX	x.xxx	0.xxx	XX.XXX	0.xxx	XX.XXX
Placebo	11	XX.XX	0.xxx	0.xxx	0.xxx						
Oxytocin	12	XX.XX	0.xxx	0.xxx	0.xxx	X.XXX	x.xxx	0.xxx	XX.XXX	0.xxx	XX.XXX
Placebo	12	XX.XX	0.xxx	0.xxx	0.xxx						
Oxytocin	Overall	XX.XX	0.xxx	0.xxx	0.xxx	x.xxx	x.xxx	0.xxx	XX.XXX	0.xxx	XX.XXX
Placebo	Overall	XX.XX	0.xxx	0.xxx	0.xxx						

¹Values are based on untransformed data unless otherwise specified

Table 25: Percentage of Heavy Drinking Days per Week – Multiple Imputation for Missing Values, Mixed Effects, Weeks 3-12

Least Squares Means

				95%	% CI			Untran	sformed
Arm	Week	Estimate	SE	Lower CI	Upper CI	Difference	SE	p-value	Cohen's d
Oxytocin	3	XX.XX	0.xxx	0.xxx	0.xxx	X.XXX	X.XXX	0.xxx	XX.XXX
Placebo	3	XX.XX	0.xxx	0.xxx	0.xxx				
Oxytocin	4	XX.XX	0.xxx	0.xxx	0.xxx	X.XXX	X.XXX	0.xxx	XX.XXX
Placebo	4	XX.XX	0.xxx	0.xxx	0.xxx				
Oxytocin	5	XX.XX	0.xxx	0.xxx	0.xxx	X.XXX	X.XXX	0.xxx	XX.XXX
Placebo	5	XX.XX	0.xxx	0.xxx	0.xxx				
Oxytocin	6	XX.XX	0.xxx	0.xxx	0.xxx	X.XXX	X.XXX	0.xxx	XX.XXX
Placebo	6	XX.XX	0.xxx	0.xxx	0.xxx				
Oxytocin	7	XX.XX	0.xxx	0.xxx	0.xxx	X.XXX	X.XXX	0.xxx	XX.XXX
Placebo	7	XX.XX	0.xxx	0.xxx	0.xxx				
Oxytocin	8	XX.XX	0.xxx	0.xxx	0.xxx	X.XXX	X.XXX	0.xxx	XX.XXX
Placebo	8	XX.XX	0.xxx	0.xxx	0.xxx				
Oxytocin	9	XX.XX	0.xxx	0.xxx	0.xxx	X.XXX	X.XXX	0.xxx	XX.XXX
Placebo	9	XX.XX	0.xxx	0.xxx	0.xxx				
Oxytocin	10	XX.XX	0.xxx	0.xxx	0.xxx	X.XXX	X.XXX	0.xxx	XX.XXX
Placebo	10	XX.XX	0.xxx	0.xxx	0.xxx				
Oxytocin	11	XX.XX	0.xxx	0.xxx	0.xxx	X.XXX	X.XXX	0.xxx	XX.XXX
Placebo	11	XX.XX	0.xxx	0.xxx	0.xxx				
Oxytocin	12	XX.XX	0.xxx	0.xxx	0.xxx	X.XXX	x.xxx	0.xxx	XX.XXX
Placebo	12	XX.XX	0.xxx	0.xxx	0.xxx				
Oxytocin	Overall	XX.XX	0.xxx	0.xxx	0.xxx	X.XXX	x.xxx	0.xxx	XX.XXX
Placebo	Overall	XX.XX	0.xxx	0.xxx	0.xxx				

Statistical Analysis Plan: Protocol NCIG-007R, Version 1.0 Dated: 7 Sep 2023

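### Under missing at random, leaving treatment out of the imputation model shrinks the only planned missing-data sensitivity analysis of the primary endpoint toward no difference (minor)

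*SAP*

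**What the plan says.** The primary analysis is a mixed model on available data in the Full Analysis Set. SAP 9.4.1 gives its terms: "Treatment group, study week, treatment group by study week interaction, clinical site and baseline percentage of heavy drinking days will be covariates". Nothing is imputed for it.

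One sensitivity analysis addresses missing data, by multiple imputation. On the imputation model, SAP 9.5.1 and Protocol 11.4.2 agree: "The imputation model will include a limited set of variables likely to be associated with missingness on the primary endpoint, excluding treatment assignment". The predictors are left open: "The variables may include but are not limited to site, time and baseline alcohol use". Protocol 11.4.2 had passed this decision on: "Specification of the variables used in the multiple imputation models will be provided in the SAP". On method, SAP 9.5.1 says "If the data have monotone missingness then the regression method will be used", with a Monte Carlo method otherwise. The "imputed datasets each will be analyzed using mixed effects models then SAS PROC MIANALYZE will be used to combine the parameter estimates".

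The output is Table 25 in SAP 12.1.2, "Percentage of Heavy Drinking Days per Week – Multiple Imputation for Missing Values, Mixed Effects, Weeks 3-12". It reports arm differences, p-values and Cohen's d by week and overall. Neither document gives a reason for excluding treatment or calls the analysis conservative.

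**The concern.** The analysis model tests treatment and treatment by week, while the imputation model is forbidden to contain either. Missing weeks in both arms are therefore drawn from a common distribution given the predictors. If the predictors are only site, time and baseline drinking, imputed values carry no arm difference. If earlier weekly outcomes are also predictors, they carry part of it.

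The SAP does not settle which case applies. Naming time as a predictor fits a layout with one row per week. The monotone rule fits one row per subject, with earlier weeks predicting later ones.

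At stake is how Table 25 is read. It exists to show whether the Table 24 result depends on the missing data. If it comes out weaker, the reader cannot tell real sensitivity from shrinkage built into the imputation model. No other planned analysis would separate the two: the untransformed model in SAP 9.4.1 addresses transformation, and the specific Brief Drinking Questionnaire rule in SAP 9.5.1 names only the two dichotomous endpoints.

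**Working it through.** **Inputs.** From SAP 7.0: d = 0.60, two-sided alpha 0.05, 50 per arm, 12% attrition, 44 per arm analysed, power 0.80. Not in the documents, and assumed here: when dropouts leave, the within-subject correlation, equal attrition by arm, and dropouts keeping the same effect as completers. No SD is given, so d is taken on the 10-week subject mean with SD 1.

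**The plan's own figure.** 0.60 × √(44/2) = 2.81, and 2.81 − 1.96 = 0.85, giving power 0.80 (0.804 by the normal approximation, 0.795 by the noncentral t). 44/0.88 = 50 per arm. The stated power is reproduced.

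**Closed form.** If a fraction f of subject-weeks is imputed with no arm information, the expected difference is 0.60 × (1 − f), where f = 0.12 × (mean weeks lost / 10). I checked this with large simulated samples (200,000 subjects, 10 weeks, dropout completely at random, exchangeable correlation 0.4 to 0.8 or first-order autoregressive 0.7 to 0.9, baseline correlation 0.4).

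| Dropout pattern | Mean weeks lost | f | 0.60 × (1 − f) | Simulated, earlier weeks not used | Simulated, earlier weeks used | Simulated, earlier weeks and treatment used |
|---|---|---|---|---|---|---|
| All of Weeks 3-12 lost | 10 | 0.120 | 0.528 | 0.524-0.532 | 0.524-0.532 | 0.598-0.605 |
| Uniform over Weeks 3-12 | 5.5 | 0.066 | 0.560 | 0.558-0.566 | 0.570-0.593 | 0.596-0.602 |
| Only the last 1 to 3 weeks lost | 2 | 0.024 | 0.586 | 0.580-0.591 | 0.593-0.604 | 0.596-0.605 |

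Adding treatment restores about 0.60 in every row, so the exclusion is the cause. Earlier maintenance weeks cannot help a subject who has none, which is why the first row does not improve when they are used.

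**Trial size, worst case.** 50 per arm, 6 per arm with no maintenance data, one outcome per subject, baseline unrelated to outcome, 20 imputations, Rubin's rules, 4,000 trials:

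| Imputation model | Mean estimate | Rubin SE | Empirical SD | Power |
|---|---|---|---|---|
| Treatment excluded | 0.532 | 0.216 | 0.189 | 0.71 |
| Treatment included | 0.605 | 0.215 | 0.219 | 0.79 |

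A separate run of the same worst case gave power 0.69 and 0.79, hence about 0.70 against about 0.79.

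**Size of the shift.** The plan implies a standard error of √(2/44) = 0.213. The worst-case shift is 0.60 − 0.528 = 0.072, and 0.072/0.213 = 0.34, about one third of a standard error.

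**False positives.** With treatment excluded, the Rubin standard error exceeds the true spread of the estimate (0.216 against 0.189), so the test is conservative. In simulations with no true effect the rejection rate was 0.020 to 0.048, so there is no inflation.

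**The case against.** The strongest reply is that bias here depends on an assumption. Subjects who only stop drug stay in the study (Protocol 7.14), missed drinking data are collected at the next visit, and the drinking interview can continue by telephone after withdrawal (Protocol 10.32, SAP 5.1.1). Missing weeks therefore come mainly from people who have left altogether, and nothing says that they keep the full drug effect. If their outcomes resemble the pooled mean, leaving treatment out is a cautious scenario. This stands in part: the shrinkage is bias only under missing at random, and the point is stated on that condition. It does not rescue the text, because neither document presents the exclusion as a cautious or not-at-random scenario.

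Second, including treatment will make Table 25 nearly repeat Table 24. That is true and should be stated in the SAP. A sensitivity analysis whose shift is set by its own model is still less informative than one that repeats the primary result for a known reason.

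Third, a run with treatment could be added in the SAP alone, since Protocol 11.1 lets the SAP add detail and exploratory analyses. That is a possible cheaper route, but the protocol would still name the version without treatment as the sensitivity analysis.

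A reader might infer that the primary result is biased, or that an estimate of 0.53 is to be expected. Neither follows. The primary model uses available data only. The 0.53 case needs every dropout to lose all ten maintenance weeks, which the rules above make unlikely, as does the rule that three observed days make a valid week (SAP 5.1.5). Claims of frequent loss of significance would need a smaller effect or higher attrition than the documents give.

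**Conclusion.** The concern holds under missing at random, and it is minor. At d = 0.60 and 12% attrition equal by arm, the imputation estimate is about 0.53 at worst, about 0.56 to 0.58 for dropout spread over Weeks 3-12 (up to 0.59 at the strongest correlation tried), and about 0.58 to 0.60 if only late weeks are lost. The lower figures apply if earlier weeks are not predictors, the higher if they are. Only attrition and d come from the documents. Timing, correlation and balance of dropout are assumptions.

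The consequence is confined to one table. The sensitivity analysis is tilted toward no difference and somewhat underpowered, so a weaker Table 25 is not by itself evidence that the primary result depends on missing data. The open predictor list also leaves undone what Protocol 11.4.2 assigned to the SAP.

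**What to change.** In SAP 9.5.1 and Protocol 11.4.2, change the exclusion of treatment to its inclusion, or impute separately by arm. Replace the open list with fixed predictors: treatment, site, baseline percentage of heavy drinking days, and the observed weekly percentages of heavy drinking days. State that the analysis assumes missing at random and will largely reproduce the primary model.

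If the sponsor wants to keep the version without treatment, report it only as a second run, labelled as a conservative scenario. A placebo-based or delta-adjusted run to test departures from missing at random is optional and would cost one more imputation run.

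The cost is a short SAP edit before unblinding and a small protocol amendment, which Protocol 13.2.2 sends to the IRB for approval before implementation and to the FDA. No new data are needed. The downside is the overlap between Tables 24 and 25.
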